13. AMENDMENTS TO THE CIP

In case of changes to the clinical trial protocol are needed, an amendment should be made. Proposed amendments to the CIP shall be agreed upon between the sponsor and principal investigator, or the coordinating investigator. Substantial amendments should be approved by the ethical committee before incorporated.

14. DEVIATIONS FROM CLINICAL INVESTIGATION PLAN

The investigator should not deviate from the clinical investigational plan except if needed to protect the rights, safety and well-being of the subjects. Such cases should be documented and reported to the EC and the Sponsor as soon as possible.

If deviations (other than mentioned above) occur, the Investigator should inform the monitor/clinical study manager and record in the protocol deviation log provided in the study site file. The implications of the deviation must be reviewed and discussed between the Sponsor and the Investigator. If deviations are found during monitoring visits, they should also be documented in the monitoring report and handled as above. This should be done as soon as possible after detection to avoid repetitive deviations. Continuous review of protocol deviations during monitoring visits aim to detect systematic errors and to identify retraining needs at the site. Frequency of monitoring is described in the monitoring plan and should be increased if systemic deviations are identified.

All protocol deviations must be documented stating the reason, date, the action(s) taken, and the impact for the subjects and/or the study.

If serious or repeated deviations occurs, the Sponsor has the right to initiate early termination of the study.

At the end of the study, protocol deviations will be categorized as minor or major and their consequence on analysis populations will be decided.

15. DEVICE ACCOUNTABILITY – IF APPLICABLE

The device used in the study (Ponto 4) is a CE marked device. In total, sixty devices will be shipped to the investigation site by Oticon Medical AB. The records for the device shipping will be stored in the Trial Master File. The serial number of the sound processors that will be fitted for each patient and used throughout the study will be noted in eCRFs. Any deficiencies related to the devices will be handled through the complaint system.

16. STATEMENTS OF COMPLIANCE

The clinical investigation will not be commenced until approval from an ethical committee and HRA has been received.

Ethical conduct of the investigation

The clinical investigation will be performed in consistency with the current version of the declaration of Helsinki (Seventh Revision 2013), and Good Clinical practice - ISO 14155 and applicable regulatory requirements.

Ethics review

The investigation plan, including the final version of the Patient Information and Consent Form must be approved in writing by an Independent Ethics Committee (IEC) before enrolment of any patient into the investigation. Substantial amendments to the Clinical Investigation Plan must be approved by the IEC if they influence the risk for the subject. Non-substantial amendments will be notified to the ethics committee.

17. INFORMED CONSENT PROCESS

The clinical investigator will ensure that the patient is given full and adequate oral and written information about the nature, purpose, possible risks and benefits involved. Patients must be notified that they are free to discontinue participation in the investigation at any time. The patient will be given time for consideration and the opportunity to ask questions before signing the informed consent form. The patient signed informed consent must be obtained before conducting any procedures specifically for the investigation.

If any new information becomes available during the course of the trial that could influence the patients' willingness to participate, the patient will be informed and asked to sign a revised informed consent.

The patient will consent in writing that the results obtained in the investigation may be used in authority assessment or submissions for publications in scientific journals with the condition that privacy and confidentiality is preserved. The patient will also consent in writing that concerned personnel, sponsor representatives and regulatory authorities may have access to the patient's medical record to perform source data verification.

The signed original of the consent form must be filed by the clinical investigator. A copy of the

Patient Information including the signed consent form should be given to the patient.

18. ADVERSE EVENTS, ADVERSE DEVICE EFFECTS AND DEVICE DEFICIENCIES

18.1 Adverse Event (AE)

Any untoward medical occurrence, unintended disease or injury or any untoward clinical signs (including an abnormal laboratory finding) in subjects, users or other persons whether or not related to the investigational medical device.

Adverse Events will be logged in the EDC system (Smart Trial), together with an assessment by the investigator, and reported as per below. AEs will be reported from the enrolment in the study. Any AEs occurring before then will be part of the subject's medical history.

NOTE 1: This definition includes events related to the investigational device or the comparator.

NOTE 2: This definition includes events related to the procedures involved.

NOTE 3: For users or other persons, this definition is restricted to events related to investigational medical devices.

The investigator shall provide adequate medical care to a subject during and after a subject's participation in a clinical investigation in the case of adverse events, as described in the informed consent.

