5. RISKS AND BENEFITS OF THE INVESTIGATIONAL DEVICE AND CLINICAL EVALUATION

The investigational device (Ponto 4) is fitted on users that are already Ponto users implanted with an abutment. Additionally, Ponto 4 will be fitted according to the manufacturer recommend fitting guidelines. Hence, the risk of participating in this study is low and comparable to corresponding rehabilitation outside this study. No risks are expected in regards to using Ponto 4 as investigational device. No disadvantages are expected for the subjects, other than the tiredness the patients can experience when listening to speech in noise and having to repeat speech. Any risk of using Ponto 4 in the patients's daily life is equal to that associated with the use of the patient's own Ponto device.

Additionally, the patient will be offered to keep the investigational device after the completion of the study if he/she wishes to do so.

There are no expected interactions of the treatment in this study with concomitant medical treatments or medication.

Three visits (of about 2 hours each) are included in this study, which is one extra visit as compared to normal standard care for patients that are switching BAHS sound processor.

It is therefore concluded that the risks associated with participation in this study are minimal and acceptable when weighed against the potential user benefits and the gain in terms of research results in a field important for long-term patient outcomes.

All adverse events will be registered and taken into consideration when compiling the final report.

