7.4 Subject population

Based on the sample size calculation reported in Sec. 12, it was decided that a total of 30 patients will be included in the study. The patients will be selected from the Queen Elizabeth Hospital database. A member of the clinical team at the hospital will perform a pre-screening by looking at the patient's journal, according to the inclusion criteria listed below. It was decided to include preferably patients that are entitled for a sound processor upgrade to reduce the burden on the patient, since patients entitled for an upgrade would need to visit the clinic anyways to get a new sound processor fitted. Only the patients that fulfil those inclusion and exclusion criteria that are available on the patient's journal will be contacted and considered suitable candidates for the study. Screening will occur at Visit 1 after the informed consent is signed. Patients that fulfil all inclusion and exclusion criteria will be enrolled in the study.

Inclusion criteria

- Minimum 18 years and maximum 70 years old.
- UK English mother tongue.
- Bilateral conductive or mixed hearing loss.
- Users fitted unilaterally or bilaterally on abutment.
- Users are currently fitted with either Ponto 3, Ponto Plus or Ponto Pro (devices with a fitting range up to 45 dB HL).
- Users with at least 6 months of daily experience with one Ponto sound processor.
- BC thresholds of the implanted ear(s) better (lower) than or equal to 40 dB HL (average of 0.5, 1, 2 and 3 kHz) based on BC in-situ measurement at the first visit.
- People currently employed/self-employed (since the Need for Recovery questionnaire refers to work-related fatigue).
- Speech recognition scores better (higher) than or equal to 50% at +4 dB SNR with OSN OFF (as assessed via the first training list at Visit 1). This is to avoid including patients that are already “giving up” at +4 dB SNR.
- Users entitled for a sound-processor upgrade (according to the investigator) will first be selected. If there are not enough users entitled for an upgrade, then patients fitted with Ponto between 7 and 12 months before visit 1 will be considered. If there are not enough users within 7-12 months, then patients fitted with Ponto between 13 and 18 months before visit 1 will be considered.

Exclusion criteria

- Single-sided deafness (SSD)
- Hearing aid or cochlear implant on the opposite ear.
- Test persons with current eye diseases and/or history of eye surgery on both eyes.

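### Section 18.1 starts adverse event reporting at enrolment, which under 7.4 can come only after Ponto 4 has been fitted and the screening list run, so post-consent events in that window are classed as medical history

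*Combined protocol and SAP*

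**What the plan says.** - **Start of reporting (18.1).** The start point and what happens to anything earlier are stated together: "AEs will be reported from the enrolment in the study. Any AEs occurring before then will be part of the" subject's medical history. There is no exception for events caused by the device or by a study procedure.
- **Screening and enrolment (7.4).** "Screening will occur at Visit 1 after the informed consent is signed", and then "Patients that fulfil all inclusion and exclusion criteria will be enrolled in the study".
- **Criteria that depend on Visit 1 procedures (7.4).** The bone-conduction threshold average must be 40 dB HL or lower on the in-situ measurement at the first visit. Speech recognition at +4 dB SNR with OSN OFF must be at least 50%, "as assessed via the first training list at Visit 1".
- **General undertaking (Section 5).** "All adverse events will be registered and taken into consideration when compiling the final report".
- **Scope of the definition (18.1, NOTE 2).** "This definition includes events related to the procedures involved".

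**The concern.** The usual purpose of a medical-history rule is to separate what the patient brought to the study from what happened in it. Here the dividing line is enrolment, and enrolment comes after the patient has consented, been fitted with the investigational device and listened through it in noise. An event in that interval, such as discomfort during the feedback measurement or a reaction to the listening task, happened in the study but would be labelled as pre-existing.

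Two things are at stake. For patients who go on to be enrolled, such events are left out of the adverse event log and attributed to the past. For patients who are fitted and then fail the threshold or speech criterion, reporting never starts, so their exposure to Ponto 4 adds nothing to the log. No efficacy endpoint or analysis is affected.

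**Working it through.** The plan gives no figure to reproduce. The check is the order of events at Visit 1, traced through the sections that fix it.

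1. **Consent comes first.** Section 17 requires signed consent before any investigation-specific procedure. Section 8.1 lists consent ahead of the fitting. From this point the patient is undergoing study activity.
2. **Ponto 4 is fitted next.** Section 8.2.3 makes the feedback measurement and the in-situ audiometry parts of the Ponto 4 fitting. Table 2 shows the in-situ result obtained under OSN Auto and copied to the other two settings. The 40 dB HL criterion therefore cannot be judged before the device is on the patient.
3. **The first training list follows.** Appendix B fixes the Visit 1 training order for all subjects, whether their ID is odd or even. The +4 dB SNR, OSN OFF list comes first and is named as the screening condition. OSN OFF is a Ponto 4 setting, and 7.3 restricts the patient's own device to questionnaire reference, so this list is heard through Ponto 4. Appendix A puts one list at about 8 minutes. It is a training list; Appendix B counts test lists separately.
4. **Eligibility can be decided only now.** Under 7.4, enrolment requires all criteria to be met, so it cannot precede the end of step 3.
5. **Reporting starts at enrolment (18.1).**

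The uncovered window therefore runs from consent to the eligibility decision. It contains the fitting, whose length is not stated, plus one list of about 8 minutes. It applies to every patient.

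**Patients who fail screening.** They never reach step 5, so all of their device exposure is outside the reporting period. The plan gives no screen-failure rate. As an illustration only, suppose a fraction f of those fitted fail the 40 dB HL or 50% criterion and 30 are enrolled. The number fitted but never enrolled is 30 × f / (1 − f):

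- f = 0.10: 30 × 0.10 / 0.90 = 3.3
- f = 0.30: 30 × 0.30 / 0.70 = 12.9

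That is about 3 to 13 people per 30 enrolled. The range is an assumption, and the finding does not depend on it.

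**Against Section 5.** Section 5 says every adverse event is registered and considered in the final report, and gives no start point. Section 18.1 removes a period after consent from reporting. A site cannot follow both for an event during the fitting.

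**The case against.** **Enrolment may simply mean consent.** Section 18 does not define the term. Two other uses, in the time-frame text of 7.4 and the ethics-review text of Section 16, require ethics approval before enrolment; they fit consent as well as they fit completed screening. This has some force, but neither passage defines enrolment, and 7.4 is the only place that says when it happens for an individual patient. If consent was meant, 18.1 and 7.4 still need reconciling.

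**Other records catch these events.** Section 10.3 requires all adverse events to be documented in the medical record, and 18.3 gives device deficiencies their own log with no enrolment limit. Both stand and reduce the harm. Neither replaces the adverse event log: the medical record is a source document, and the deficiency log covers faults in the device, not harm from a device or procedure working as intended.

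**The risk is low.** The device is CE-marked, the patients are experienced Ponto users, and Section 5 rates the risk as comparable to ordinary rehabilitation. This stands, and it limits the size of the point.

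A reader might also infer three stronger things that the documents do not support:

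- *That 18.1 contradicts its own notes.* The notes say which kinds of event count; the enrolment sentence says when reporting begins. Scope and start date do not conflict.
- *That an event in a screen failure is not an adverse event at all.* The definition reaches beyond enrolled subjects, NOTE 3 keeps device-related events in users and others within it, and the sentence at issue itself calls the earlier events AEs. What is limited is the reporting.
- *That all such events escape the 24-hour and authority reports.* Under 18.7 those routes take serious adverse events, device deficiencies that might have led to one, and updates. A non-serious event would not go there whatever the start date. Deficiencies are logged independently. For a serious event, 18.7 sets no enrolment condition, so exclusion is arguable, not established.

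**Conclusion.** The point holds. Read with 7.4, the start date in 18.1 falls after the first use of the investigational device. Post-consent events in that window are assigned to medical history, and patients who fail screening after fitting never enter the reporting period. This is a stated rule that gives a wrong result and conflicts with Section 5; it is not merely a missing detail.

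The size is small. The window is part of one supervised visit, serious events in it are unlikely, and any effect on expedited reporting is confined to serious adverse events. The loss is in the completeness of the log and the attribution of events. The conclusion rests on taking 7.4 at its word on when enrolment occurs. A correction is worth making because it costs almost nothing.

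**What to change.** - In 18.1, start adverse event reporting at signature of the informed consent form. Alternatively, define enrolment as signed consent and bring 7.4 into line with that definition.
- Limit medical history to events that began before consent.
- State that events in patients who fail screening after Ponto 4 has been fitted are logged in the same way and, where they meet 18.7, reported on the 18.8 timelines.

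The cost is a short edit to 18.1 (and to 7.4 if the second route is taken), an adverse event form opened at consent, and a few extra entries, some of them for people who are never enrolled.

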18.2 Serious Adverse Event (SAE)

Adverse event that:

- a) led to a death, injury or permanent impairment to a body structure or a body function.
- b) led to a serious deterioration in health of the subject, that either resulted in:
 - a life-threatening illness or injury, or
 - a permanent impairment of a body structure or a body function, or
 - in-patient hospitalization or prolongation of existing hospitalization, or
 - in medical or surgical intervention to prevent life threatening illness
- c) led to foetal distress, foetal death or a congenital abnormality or birth defect.

NOTE 1: Planned hospitalization for pre-existing condition, or a procedure required by the Clinical Investigation Plan, without a serious deterioration in health, is not considered a serious adverse event.

18.3 Device deficiency

Inadequacy of an investigational medical device related to its identity, quality, durability, reliability, safety or performance. This may include malfunctions, use error, or inadequacy in the information supplied by the manufacturer. Device deficiency's will be logged in the EDC system (Smart Trial) together with an assessment by the investigator, in the Device deficiency's log and reported as per 18.7 and 18.8 where applicable.

18.4 Adverse Device Effect (ADE)

Adverse event related to the use of an investigational medical device.

NOTE 1- This includes any adverse event resulting from insufficiencies or inadequacies in the instructions for use, the deployment, the implantation, the installation, the operation, or any malfunction of the investigational medical device.

NOTE 2- This includes any event that is a result of a use error or intentional abnormal use of the investigational medical device.

18.5 Serious Adverse Device Effect (SADE)

Adverse device effect that has resulted in any of the consequences characteristic of a serious adverse event.

18.6 Unanticipated Serious Adverse Device Effect (USADE)

Serious adverse device effect which by its nature, incidence, severity or outcome has not been identified in the current version of the risk analysis report.

NOTE: Anticipated SADE (ASADE): an effect which by its nature, incidence, severity or outcome has been previously identified in the risk management process as per ISO14971.

18.7 Reportable Events

In accordance with the applicable regulatory guidelines and directives, the following events are considered reportable events;

- any SAE,
- any Device Deficiency that might have led to a SAE if:
 - a) suitable action had not been taken or
 - b) intervention had not been made or
 - c) if circumstances had been less fortunate
- new findings/updates in relation to already reported events.

Reportable events shall be reported to the sponsor using the applicable forms as per timelines stated under 18.8.3.

Emergency contact for reporting SAEs and/or SADEs

Oticon Medical
[name],
[name]
Vigilance number: [contact]
Mail: [contact]

18.8 Reporting Timelines

18.8.1 Reports to the National Competent Authority

The sponsor is responsible to report to applicable competent authorities according to national regulations. All reportable events as described in 18.7 which indicate an imminent risk of death, serious injury, or serious illness and that requires prompt remedial action for other

patients/subjects, users or other persons or a new finding to it: **immediately, but not later than 2 calendar days** after awareness by sponsor of a new reportable event or of new information in relation with an already reported event.

- any other reportable events as described in 18.7 or a new finding/update to it: **immediately, but not later than 7 calendar days** following the date of awareness by sponsor of the event.

The investigator is responsible to report to regulatory authorities regarding serious adverse events and device deficiencies that could have led to a serious adverse device effect, as required by the national regulations. Further, the sponsor is responsible to inform regarding any new significant information about the clinical investigation to the CA.

18.8.2 Reports to the ethical committee

The investigator is responsible to report to the EC serious adverse events and device deficiencies that could have led to a serious adverse device effect.

18.8.3 Report by the investigator to the sponsor

Reportable events should be reported to Oticon Medical **within 24 hours** from when Investigator is first made aware of the event using reportable events forms. It is the responsibility of the investigator to supply the sponsor, upon sponsor's request, with any additional information related to the safety reporting of an event without unjustified delay.

19. PUBLICATION POLICY

This study will be registered on ClinicalTrials.gov.

The investigator is free, and is encouraged, to publish the data from the study at scientific conferences and publications. For completion of these publications, the investigators will be primarily responsible, and Oticon Medical will assist the investigators in the process. No publications will be made without the final approval of the sponsor. Privacy and confidentiality of information about each subject will be preserved in the report and any publication of the clinical investigation data.

Oticon Medical will have the right to collect the data, and, if applicable, compare results with similar studies from other centres and publish such aggregated analyses. No publications will be made without the final approval of the investigators.

APPENDIX A: ALL TEST CONDITIONS

It is estimated that testing one list will take about 8 minutes. For time estimate per person/ visit please see appendix B.

Condition	Visits 1	Visit 2	Visit 3	SNRs [dB SNR]	Total no. lists	Baseline [s]	Estimated time [min]
Training lists 1	X		X	+4 (OSN OFF) -4 (OSN ON)	2	Silence: 3 s Noise: 3 s	16
Training list 2		X		+4 (OSN OFF)	1	Silence: 3 s Noise: 3 s	8
OSN OFF	X	X		-8, -4, 0, +4, +8	5	Silence: 3 s Noise: 3 s	40
OSN ON	X	X		-8, -4, 0, +4, +8	5	Silence: 3 s Noise: 3 s	40
OSN Auto	X	X	X	+4	1	Silence: 2 s Noise: 6 s	8
OSN OFF			X	+4	1	Silence: 2 s Noise: 6 s	8

APPENDIX B: BALANCED DESIGN ACROSS VISITS AND TIME ESTIMATE**VISITS 1 and 2**

- Subjects with **even ID number**, will perform

Visit 1 as follows:

- 2 training lists
- 6 test lists

Hence, 8 lists will be tested in total for a total testing time of 64 minutes. About 1 h 25 min should be taken into account to conduct pupillometry at Visit 1 (including breaks).

Visit 2 as follows:

- 1 training lists
- 5 test lists

Hence, 6 lists will be tested in total for a total testing time of 48 minutes. About 1 h 05 min should be taken into account to conduct pupillometry at Visit 2 (including breaks).

- Subjects with **odd ID number**, will perform

Visit 1 as follows:

- 2 training lists
- 5 test lists

Hence, 7 lists will be tested in total for a total testing time of 56 minutes. About 1 h 15 min should be taken into account to conduct pupillometry at Visit 1 (including breaks).

Visit 2 as follows:

- 1 training lists
- 6 test lists

Hence, 7 lists will be tested in total for a total testing time of 56 minutes. About 1 h 15 min should be taken into account to conduct pupillometry at Visit 2 (including breaks).

Visit 1 (even ID no.); Visit 2 (odd ID no.)										
	OSN ON					OSN OFF				
SNRs (dB)	-8	-4	0	4	8	-8	-4	0	4	8
Training (fixed order)		X*							X	
Test -8,0,8 (Randomized order)	X		X		X	X		X		X

* Only to be performed at Visit 1

Visit 1 (odd ID no.); Visit 2 (even ID no.)

	OSN ON					OSN Auto	OSN OFF				
SNRs (dB)	-8	-4	0	4	8	4	-8	-4	0	4	8
Training (fixed order)		X*									X
Test -4, 4 (Randomized order)		X		X		X		X		X	

* Only to be performed at Visit 1

Additionally, the following applies:

- The first OSN setting (ON or OFF) at visit 1 and 2 will be balanced between subjects (50% of the subjects will start with OSN ON and 50% of the subjects will start with OSN OFF – see Figure 1).
- The presentation order of SNRs will be randomized within each OSN setting.
- The OSN Auto condition will be presented either at Visit 1 or at Visit 2 – in between the two other settings (see Figure 1).
- The training for Visit 1 is performed in a fixed order: first +4 dB SNR with OSN OFF (relatively easy condition and condition used for screening), then -4 dB SNR with OSN ON (relatively more difficult condition).

VISIT 3

- At the third visit, 4 lists will be tested in total (including training) for a total testing time of 32 minutes. About 45 minutes should be taken into account to conduct pupillometry at the third visit (including breaks).

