6. OBJECTIVES AND HYPOTHESES

6.1 Primary Objective and hypothesis

- The primary objective of this study is to evaluate the decrease in pupil dilation when listening to speech-in-noise with OSN ON compared to OSN OFF at +4 dB SNR. The hypothesis is that OSN ON will lead to a significant reduction in pupil dilation (i.e., less listening effort) as compared to OSN OFF.

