12. STATISTICAL CONSIDERATIONS

The analysis of the primary endpoint will be performed via Growth Curve Analysis (Mirman, 2014) to compare the overall pupil dilation for OSN ON vs. OFF at +4 dB SNR. Growth Curve Analysis will also be used to evaluate differences in overall pupil dilation between OSN ON and OSN OFF at different SNRs, between OSN Auto and OSN OFF (before and after field trial), and between OSN Auto and OSN ON at +4 dB SNR.

Additionally, a mixed-model ANOVA (SNR and OSN setting as fixed factors; subject as random factor) will be used to analyze the peak pupil dilation (PPD) across SNRs. Only data of those patient that completed both Visit 1 and Visit 2 will be included in the final analysis. When applicable, post-hoc analysis will be performed via contrasts of least-square means to clarify at which SNRs the effect of OSN is significant (the p-values will be corrected for multiple comparisons using the Tukey method).

A mixed-model ANOVA (SNR and OSN setting as fixed factors; subject as random factor) will also be used to analyze the speech recognition scores across SNRs. When applicable, post-hoc analysis will be performed via contrasts of least-square means to clarify at which SNRs the effect of OSN is significant (the p-values will be corrected for multiple comparisons using the Tukey method).

A mixed model ANOVA will also be used to analyze the SSQ scores for Ponto 4 vs. own device, as well as for Ponto 4 at 1-month follow up vs. 3-months follow up.

A paired t-test or Wilcoxon sign-rank test will be used to compare the NfR scores with Ponto 4 compared to own device. Pearson's or Spearman's correlation between NfR scores and pupil dilation with Ponto 4 after field trial will be performed.

A Wilcoxon sign-rank test (two tailed) will be performed for each item of the preference questionnaire to test whether the distribution of the scores is significantly different than "No preference".

On all tests a significance level of 5% will be adopted. Correction for multiple comparisons will be performed where applicable.

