12.1 Sample size calculation

The sample size calculation was based on the primary endpoint. The effect size was estimated based on the interim results of a pilot study conducted internally at Oticon Medical (Denmark) - internal study reference: BC102 - where the experimental setup was the same as in the current study. Although the speech target consisted of Danish sentences (HINT; Nielsen and Dau, 2011) instead of UK English sentences as in the current study, we expect a similar effect size. Hence, an effect size of 0.48 was estimated based on the mean and standard deviations obtained for N = 20 subjects at an SNR of +4 dB (Mean with OSN ON = 0.078; Mean with OSN OFF = 0.11; standard deviation with OSN ON = 0.09; standard deviation with OSN OFF = 0.08). These mean peak pupil dilations are in line with the results obtained in a previous study that used similar setup and conditions – although the patients wore hearing aids instead of BAHS (Wendt et al., 2017). Using a significance level of 0.05 and a statistical power of 0.8, a minimum sample size of 29 subjects was obtained. Hence, it was decided that 30 subjects should complete the primary endpoint (Visit 1 and Visit 2). If test persons are withdrawn from the study, the recruitment process will continue until 30 patients have completed Visit 1 and Visit 2.

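### The order of the OSN ON and OFF blocks is balanced by design, but nothing in Section 12 ensures it is modelled, so a first-versus-second-block shift would go into the error term

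*Combined protocol and SAP*

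**What the plan says.** **Design.** Appendix B fixes the order balance for Visits 1 and 2: "50% of the subjects will start with OSN ON and 50% of the subjects will start with OSN OFF". The Auto list sits between the two blocks at the visit that carries the +4 dB lists, and even or odd ID decides which visit that is. Visit 3 balances Auto-first and OFF-first in the same way. Section 7 puts all OSN settings for a given SNR in the same visit.

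**Analysis.** For peak pupil dilation (PPD) and for speech recognition, Section 12 specifies mixed-model ANOVAs with "SNR and OSN setting as fixed factors; subject as random factor". For the primary endpoint it says only this: "The analysis of the primary endpoint will be performed via Growth Curve Analysis". It gives no fixed or random terms for that model. No analysis mentions block, order, sequence or visit.

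**Sample size.** Section 12.1 states that "an effect size of 0.48 was estimated" from the pilot ("Mean with OSN ON = 0.078; Mean with OSN OFF = 0.11"; "standard deviation with OSN ON = 0.09; standard deviation with OSN OFF = 0.08"). "Using a significance level of 0.05 and a statistical power of 0.8", it arrives at 29 and plans for 30 completers of Visits 1 and 2.

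**The concern.** Counterbalancing protects the mean difference from a time trend within the visit. It does not take the trend out of the residual; only a model term does that. If the second block runs higher or lower than the first by some amount, half the patients' ON-OFF differences move up by that amount and half move down. An analysis without block position treats this spread as patient-to-patient noise.

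Such a shift is plausible here. Section 5 expects tiredness from the task, and Section 7 names fatigue and motivation as influences to be controlled. At the visit with -4 and +4 dB, five test lists run as two in the first block, then Auto, then two in the second. The two +4 dB lists therefore start two to four lists apart, which is 16 to 32 minutes at the 8 minutes per list given in Appendix A, before breaks.

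What is at stake is efficiency, in a sample with one patient to spare over the calculated minimum. There is also some exposure to bias if order is unequal among the patients analysed. Section 12 limits the final analysis to patients who completed Visits 1 and 2. Drop-outs are replaced, but no rule gives a replacement the vacated order.

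**Working it through.** **1. Inputs from Section 12.1.** ON-OFF difference: 0.11 - 0.078 = 0.032. Effect size 0.48. Read as a paired effect size, it implies an SD of the difference of 0.032/0.48 = 0.0667. With SDs of 0.09 and 0.08, the implied correlation is (0.0081 + 0.0064 - 0.00444)/(2 × 0.09 × 0.08) = 0.70. The documents do not state this correlation.

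**2. The plan's own figure.** A paired t-test (noncentral t, 5%, effect size 0.48) needs 29 patients one-sided, with power 81%. Two-sided it needs 37. The stated 29 is therefore reproduced one-sided only. The plan does not state sidedness for the primary test, though the hypothesis is directional ("OSN ON will lead to a significant reduction in pupil dilation"). Power at n = 30 is 82% one-sided and 72% two-sided. The gap between these two figures comes from sidedness, not from block order.

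**3. Effect of an unmodelled shift.** Let π be the second-minus-first-block shift. With 15 patients in each order, each ON-OFF difference has mean δ + π or δ - π.
- The mean over 30 patients is still δ, because π cancels.
- The expected sample variance becomes 0.0667² + π² × 30/29.
- With a block term, π is removed and the residual has 28 instead of 29 degrees of freedom.

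Example for π = 0.032: the variance ratio is 1 + (0.032/0.0667)² × 30/29 = 1 + 0.2304 × 1.0345 = 1.238, so the standard error is √1.238 = 1.11 times as large.

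**4. Power at n = 30.** These figures are simulated with an exact 15/15 split, because the shift enters the estimated variance but not the sampling variance of the mean. The shift sizes are assumptions.

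| Shift | Share of 0.032 | Variance ratio | Power without block term, two-sided | One-sided | Type I error without block term, two-sided |
|---|---|---|---|---|---|
| 0 | 0 | 1.00 | 72% | 82% | 5.0% |
| 0.016 | 0.50 | 1.06 | 70% | 81% | 4.4% |
| 0.020 | 0.62 | 1.09 | 69% | 80% | 4.1% |
| 0.032 | 1.00 | 1.24 | 64% | 77% | 3% |
| 0.050 | 1.56 | 1.58 | 53% | 69% | 1.5% |

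With the block term, power stays at about 72% two-sided and 82% one-sided for every shift. If there is no shift, the term costs about 0.1 point (71.9% to 71.8% two-sided, by noncentral t).

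**5. If the pilot SD already contains the shift.** The shift-free SD is then √(0.0667² - π²). Power without the term stays at 82% one-sided (72% two-sided). Adding the term raises it to 84% (74%) at a shift of 0.016 and to 90% (83%) at 0.032.

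**6. Unequal order among analysed patients.** With k of 30 patients in one order, the bias is (2k - 30)/30 of the shift. A 16/14 split gives 2/30 = 7% and an 18/12 split gives 6/30 = 20%. At a shift of 0.032 these are about 0.002 and 0.006. A block term removes this bias as well.

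**Limit of the check.** A paired t-test on one value per patient stands in for the Growth Curve intercept contrast. Section 12.1 describes the pilot means as peak dilations, whereas the primary endpoint is overall dilation.

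**The case against.** Four arguments on the other side have weight.

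- **The shift size is unknown.** No document gives one. Up to half the OSN difference the loss is one or two points. The large losses need a shift that matches or exceeds the whole effect; 0.050 is 45% of the mean OFF response of 0.11. This stands: the table shows sensitivity and is not a forecast.
- **The pilot may already include it.** Section 12.1 says the pilot used the same experimental setup. If its order also varied and was not modelled, 0.48 already carries the shift and planned power is not eroded. This stands too. The documents do not settle which case applies.
- **The design already controls for time trends.** Same-visit testing, counterbalancing, breaks and the mix of easy and difficult SNRs all help. They protect the mean, but they do not take a remaining shift out of the residual.
- **Replacement limits imbalance.** Small splits give small bias, as step 6 shows. No rule restores the order balance, however, so an uneven split remains possible.

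A reader might infer three stronger points that the documents do not support. First, that the primary model leaves order out: its terms are simply not listed, and the explicit factor list belongs to the two ANOVAs. Second, that visit should be adjusted for in the primary contrast: Section 7 puts ON and OFF at +4 dB in the same visit, so visit cancels within each patient. Third, that the executed order is already in the data: Section 7 describes a per-patient randomization of SNRs, but no section says that the block order as run is recorded, and the list in Section 7.2.1 does not include it.

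**Conclusion.** The point holds as a matter of efficiency and robustness. The design balances block order. The PPD and speech ANOVAs leave it out, and the primary Growth Curve model is not specified closely enough to show whether it is in.

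With balanced order the ON-OFF estimate is valid and the test errs on the conservative side, so this is not a bias finding. Bias arises only if order is unequal among the patients analysed, and it is then a fraction of the shift.

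The loss ranges from one or two points of power for a shift of half the OSN difference to about 8 points two-sided (5 one-sided) for a shift equal to it. This assumes that 0.0667 is free of any shift, that n = 30, and that the paired t-test approximates the Growth Curve contrast. If 0.0667 already includes the shift, there is no shortfall against planned power, only precision left unused. The change is worth making before analysis because it costs almost nothing, and because naming the term in advance removes a later choice between adjusted and unadjusted results.

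**What to change.** In Section 12:

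1. List the terms of the primary Growth Curve model, and include block position (first or second OSN block within the visit) as a fixed effect.
2. Add the same term to the PPD and speech-score ANOVAs, and to the Visit 3 Auto/OFF model.
3. Add visit (1 or 2) as a fixed effect only in the models that run across SNRs, where the SNRs are split between two visits.
4. State that the block order as actually run is kept in the analysis dataset for each patient and visit.

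The cost is a few lines of text and one or two degrees of freedom, or about 0.1 point of power if there is no shift. Visits, patient numbers and test procedures do not change. Recording the executed order is a small data-management step if it is not already done.
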